### **Subject privacy**

HIPPA privacy rules will be observed. Subjects will be interviewed in a private room. All study testing will be conducted in closed areas.

### **Institutional Review Board procedures**

Human research must be reviewed by a convened meeting of the IRB unless the research is determined to be exempt or is eligible for expedited review. The final review category and submission requirements will be determined by the IRB. The work of reviewing submissions is divided among eight IRBs. IRBs 1 through 5 and IRB 7 review general medical research. IRB 8 reviews social and behavioral research. IRB 6 serves

Pennsylvania Hospital. If the protocol requires review by the full IRB at a convened meeting, the PI will be notified of the assignment of the protocol to an appropriate IRB within two days of receipt by the IRB. An expedited review consists of a review of research involving human subjects by the appropriate IRB executive chair or his/her designee. In reviewing the research, the reviewer may exercise all of the authorities of the convened IRB except that the reviewer may not disapprove the research. Additionally, the reviewer may refer the application to the convened IRB for a standard review as warranted.

In general, this assignment will be to the next scheduled meeting of an appropriate IRB (provided that the submission is complete). The IRB will review no more than 25 agenda items at each meeting (including new submissions, continuing reviews, amendments, unanticipated problems posing risks to subjects or others, or previously tabled protocols). Agenda items in excess of 25 will be assigned to the next scheduled meeting of an appropriate IRB.

The IRB application for continuing review must be submitted no later than six weeks prior to the expiration date for convened board review and no later than two weeks for expedited review.

**NOTE:** No research related activities may occur after the protocol expiration date unless the PI contacts the IRB and the IRB executive chair (or authorized designee) determines that it is in the best interest of subjects to continue during the lapse in IRB approval. Federal regulations require that modifications in approved research, during the period for which approval has already been given, may not be initiated without prior IRB review and approval except where necessary to eliminate apparent immediate hazards to human subjects. Sometimes modifications are noted or recognized after they occur. These changes will be reviewed by the IRB as events that may represent unanticipated problems involving risks to participants or others and to determine whether the change was consistent with ensuring the participants' continued welfare. The IRB categorizes modifications into three types: amendments, deviations, and exceptions.

### **Consent process**

The study coordinator will provide a prospective subject with an explanation of the study in person or by phone (If possible the coordinator will mail or email the consent to the prospective subject). If the subject verbally agrees during the phone screening the study team will then schedule an appointment during which the consent will be reviewed and signed after all questions have been answered. A signed copy of the consent form will be given to the participant. Informed consent documents will be stored in a secured location where the study team only has access to them. If changes are made to the consent or study procedures, participants will be required to re-consent. If the subject decides not to participate, they are free to leave the study at any time. Withdrawal will not interfere with future care.

### **Analyses**

**Axial stiffness and failure strength:** To estimate the axial stiffness of cortical bone (CB), trabecular bone (TB) and whole bone (WB) section compressive loading will be simulated in the linear elastic regime. Here, 1% axial strain will be applied to the proximal face of the  $\mu$ FE model while keeping the distal face constrained in the axial direction while assuming frictionless conditions along the transverse directions. The  $\mu$ FE models will then be solved for all three bone-compartments (CB, TB and WB). Axial stiffness is obtained as the ratio of the stress on the proximal face to the applied strain. Failure strength will be estimated assuming that bone fails when a significant portion (2%) is strained beyond the tissue yield strain chosen as 0.7%. In addition, 3D strain-energy maps will be created from upsampled images and histograms generated.

**Vertebral bone marrow adiposity:** An average fat volume fraction will be computed for each of the five lumbar vertebrae as " $f = V_f / (V_f + V_w)$ " where  $V_f$  and  $V_w$  are the voxel volumes of fat and water, each computed as an average of the four central voxels, via Eqs. 1 and 2. Relaxation times for computing saturation factors will be mean values obtained from the data collected under Aim 1 in a sub-group of subjects.

**Descriptive statistics:** To describe participant's baseline characteristics and study outcome measures at baseline and one-year follow-up, data will be recorded overall and within each treatment group. Baseline characteristics will include distribution of age, race/ethnicity, adherence data and outcome variables. Summary

statistics (standard deviations, medians, and ranges) will be tabulated for all measured variables and their frequencies computed. Graphical methods including stem-and-leaf diagrams and box plots will be used to examine distributions, identify potential influential points, and guide in the choice of transformations if warranted. Baseline measures across the treatment groups will be compared using appropriate 2-sample tests including tests, Wilcoxon rank-sum tests and Fisher's exact tests. All analyses will be conducted using Stata 9.0 and SAS (for analysis of adherence data) with two-sided tests of hypotheses and a p-value < 0.05 indicating significance. Changes in primary and secondary outcomes within patients over the 12-month study period will be calculated as differences within subjects and as % changes.

**Outcome analyses:** All analyses will be done according to the *intention to treat* principle. The primary endpoint is the change in distal tibia trabecular bone whole-section axial failure strength over the 12-month study interval. The primary hypothesis to be tested is that treatment with the active LMMS device results in greater change in this parameter than treatment with the placebo device over a 12-month period. The secondary hypothesis to be tested is that vertebral marrow adiposity is reduced in the treatment relative to the control subjects. To evaluate the changes from baseline within groups, 2-sided paired t-tests will be performed for both groups. Unpaired t-tests will be used to test the primary and secondary hypotheses that the means of the temporal changes are different between treatment groups. Linear regression models will also be constructed to compare mean within-subject changes between groups. These models will include differences within subjects as the outcome variable, and an indicator variable for treatment group and baseline measurement as the covariates. In this manner we will be able to evaluate whether the treatment effect is associated with baseline values. Further, since the efficacy of LMMS treatment has been shown to critically hinge on adherence, post-hoc analyses will be performed by considering adherence, for example, by excluding data from subjects with the lowest quartile of compliance. Lastly, we will examine the hypothesis that the treatment effect scales with compliance using regression analysis.

**Secondary analyses:** Other parameters evaluated comprise various measures of stiffness and strength analyzed from the MRI-derived  $\mu$ FE data, as well as structural measures (trabecular parameters of scale and topology at the distal site) and bone densitometry quantities, defined previously. Besides axial trabecular failure strength and stiffness, these parameters will also be computed for the cortical compartment and whole bone (comprising trabecular and cortical bone) at the peripheral location (distal tibia) and the effects compared. Since  $\mu$ FE simulations also yield strain energy maps, from histograms of this parameter, means, median and mode will be computed as any of these could be more sensitive indicators of treatment than whole-section stiffness. Densitometric variables will be evaluated as well for the locations examined (proximal femur and L-spine by DXA), and distal tibia, and 38% tibial shaft (pQCT). Appropriate adjustments will be made for multiple comparisons to account for loss of power. Lastly, associations between baseline parameters as well as between the temporal changes in these parameters will be examined by linear regression.

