## **Primary outcome variable(s)**

Increased trabecular and cortical stiffness and failure strength, assessed at the distal tibia by MR image-based FE modeling.

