## **Subjects randomized by Penn researchers**

83 (to reach final sample of 64 completers)

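### The primary hypothesis is tested without baseline adjustment although a baseline-adjusted regression is already planned, and that regression cannot show what the plan says it will

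*Combined protocol and SAP*

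**What the plan says.** All of the relevant text is in the Analyses section of the combined protocol and SAP.

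- **Primary test.** Outcome analyses names one primary endpoint, the 12-month change in trabecular failure strength at the distal tibia, and one secondary hypothesis, on vertebral marrow adiposity. Both go to the same test: "Unpaired t-tests will be used to test the primary and secondary hypotheses that the means of the temporal changes are different between treatment groups". No covariate is named.
- **Regression.** The next sentence adds: "Linear regression models will also be constructed to compare mean within-subject changes between groups". The model is specified: "These models will include differences within subjects as the outcome variable, and an indicator variable for treatment group and baseline measurement as the covariates". It is not called primary, supportive or sensitivity.
- **Purpose given for the regression.** "In this manner we will be able to evaluate whether the treatment effect is associated with baseline values".
- **Scale of change.** Descriptive statistics says that changes in primary and secondary outcomes "will be calculated as differences within subjects and as % changes", and that plots may "guide in the choice of transformations if warranted". Outcome analyses does not say which scale the t-test uses.
- **Size.** The number randomized is given as "83 (to reach final sample of 64 completers"), with 1:1 allocation. No effect size, standard deviation, correlation or power accompanies it.

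**The concern.** There are two main issues and one minor one.

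1. **Precision.** The baseline scan is collected and the adjusted model is already written down, yet the hypothesis is assigned to a test that does not adjust for baseline. With about 32 completers per arm there is little precision to spare.
2. **A claim that the model cannot support.** Whether a treatment effect varies with baseline is a question about interaction. A model with an arm term and a baseline term forces the same treatment effect at every baseline value. Its baseline coefficient describes how change relates to baseline across both arms together and says nothing about the treatment effect.
3. **Minor: scale.** Two versions of change are computed and neither is explicitly tied to the t-test. Settling this after the data are seen would raise the type I error slightly.

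**Working it through.** **Inputs from the documents.** 64 completers allocated 1:1, so n = 32 per arm; two-sided 0.05; the t-test and the regression as described. There is no stated power figure to reproduce.

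**Assumed inputs.** Correlation rho between baseline and 12 months, 0.5 to 0.98; equal variances at the two visits; treatment effect of 0.70 SD of change; completers only. The 83 − 64 = 19 participants (19/83 = 23%) not expected to complete are not modelled, and neither test resolves how they should be handled.

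**Step 1: variance.** With baseline SD s0 and 12-month SD s1:

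- variance of change = s0² + s1² − 2·rho·s0·s1
- residual variance after baseline adjustment = s1²(1 − rho²)
- difference = (s0 − rho·s1)², which is never negative

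With s0 = s1 the ratio (regression to t-test) is (1 − rho²)/[2(1 − rho)] = (1 + rho)/2. Estimating the extra coefficient multiplies this by about 1 + 1/(2n − 4) = 1 + 1/60 = 1.0167.

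**Step 2: power from the noncentral t.** For the t-test the noncentrality is 0.70 × √(32/2) = 2.80 with 62 df, giving 78.7%. For the regression it is 2.80/√(ratio) with 61 df. The last column is the smallest n per arm at which the t-test matches the regression at n = 32.

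| rho | (1+rho)/2 | × 1.0167 | noncentrality | regression power | t-test n per arm to match |
|---|---|---|---|---|---|
| 0.5 | 0.750 | 0.7625 | 3.207 | 88.4% | 42 |
| 0.8 | 0.900 | 0.915 | 2.927 | 82.1% | 35 |
| 0.9 | 0.950 | 0.966 | 2.849 | 80.1% | 34 |
| 0.95 | 0.975 | 0.991 | 2.812 | 79.0% | 33 |
| 0.98 | 0.990 | 1.007 | 2.791 | 78.4% | none needed |

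The two analyses have equal power at rho = 0.966.

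**Step 3: the case of no gain.** The difference in Step 1 is zero when s0 = rho·s1, that is, when change is unrelated to baseline. The ratio is then 1.0167, the noncentrality 2.80/√1.0167 = 2.777, and the power 78.0% against 78.7%, a loss of 0.7 point.

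**Step 4: the interaction claim.** The model as written is: change = a + b·arm + c·baseline. The treatment effect is b at every baseline value. Dependence on baseline needs a further term, d·arm×baseline, which the plan does not list.

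**Step 5: scale of change.** Simulation under the null used bivariate normal data, 32 per arm, baseline CV 15% or 25% (assumed), rho 0.5 to 0.98 and 200,000 trials per cell. Each single test rejects in 4.8 to 5.1% of trials. Claiming whichever of the absolute and percent t-tests is significant rejects in 5.6 to 6.3%. Which scale has more power depends on the model for variability:

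- Additive normal noise, additive effect of 0.70 SD of change: percent change has about 65 to 77% power, against 78.7% for absolute change.
- Lognormal data with equal log-variances at both visits and an effect of 0.70 SD of log change: percent change has 77.6 to 78.8%. At rho 0.98 and CV 25% the powers are percent 78.3%, absolute 76.4%, regression 75.8%.

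**The case against.** The strongest reply is that the plan already assigns one test to one endpoint, that the test is valid, and that the adjusted estimate will be produced anyway. On this view, changing the primary analysis is a preference. Much of this stands. The word introducing the regression marks it as additional, and a reader who infers bias, or an undefined primary test, goes further than the text allows.

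The gain also depends on quantities that the documents do not give. At rho 0.9 it is 80.1 − 78.7 = 1.4 points, and at 0.95 it is 0.3. At rho 0.5 an effect of 0.70 SD of change equals 0.70 SD of baseline, which is 10.5% of mean strength at CV 15% and 17.5% at CV 25%. Nothing in the documents favours 0.5 over 0.95. If variability is multiplicative and percent change is independent of baseline, simulation gave the regression 0.2 to 0.6 points less power than the absolute t-test.

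On scale, the percent-change and transformation remarks both sit under Descriptive statistics, and the regression takes the within-subject difference as its outcome. Absolute change is therefore the natural reading.

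Two stronger readings are tempting and should not be drawn. A reader might infer that the sponsor could claim success on the absolute t-test, the percent t-test or the regression, with a correspondingly larger type I error; the plan contains no such procedure. A reader might also infer that percent change always costs power; Step 5 shows that this holds under additive noise but not in general.

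The main-effects point is not answered by any of this.

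**Conclusion.** The point holds as a matter of precision and specification. The unadjusted t-test is valid and is in effect the primary test. Replacing it with the regression already planned would gain 9.7 points of power at rho 0.5, 3.4 at 0.8 and 1.4 at 0.9. It would gain nothing above about 0.97, or if change is unrelated to baseline, with a loss of under about 1 point there. These figures rest on assumed equal variances, an assumed effect of 0.70 SD of change, and 32 completers per arm; the true gain for this trial cannot be known from the documents.

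The statement that the main-effects regression can show whether the effect depends on baseline is wrong as written, whatever the assumptions.

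The unstated scale is minor: about 0.6 to 1.3 points of type I error under the normal model, and only if the scale were chosen after seeing the data. The change is worth making because it is cheap, not because the present test is unsound.

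**What to change.** Before unblinding, amend the Outcome analyses paragraph as follows.

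- Make the primary analysis the linear regression of absolute 12-month change in distal tibia trabecular failure strength on treatment arm and baseline value, main effects only. Report the treatment coefficient, its 95% confidence interval and the two-sided p-value as the primary result.
- Use the same model for vertebral marrow adiposity.
- Label the unpaired t-test and all percent-change analyses supportive.
- Remove the statement that this model assesses dependence of the effect on baseline. Put that question in a separate exploratory model with a treatment-by-baseline term.

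If the sponsor prefers to keep the t-test as primary, the minimum is to state that it uses absolute change, label the regression supportive, and correct the sentence on dependence on baseline.

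The cost is a few sentences and no new data. Statistically it is one degree of freedom and, in the unfavourable cases, a fraction of a percentage point of power.

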## **Target population**

Post-menopausal female subjects ages 45-65 years who have a history of amenorrhea for a minimum of 24 months and a serum FSH of 25 or greater.

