## **Key inclusion criteria**

Females, ages 45-65 years in post-menopause, as defined by a history of amenorrhea for a minimum of 24 months and a serum FSH concentration of 25 mIU/mL and negative pregnancy test

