Randomization and blinding: Subjects meeting the entry criteria at the screening visit will be randomly allocated 1:1 to an active LMMS or a placebo device. The subjects will then be assigned a treatment number. Participant's names and study numbers will be kept in a password-protected database separate from other study records. Random numbers will be generated by a random number generator by the unblinded device manager who will maintain a database with even numbers being assigned to treatment and odd numbers to placebo. This database will not be shared with the PI or other members of the study team before completion of the study. The project manager will be responsible for storing the Juvent devices and the device manager will be responsible for dispensing them to the study staff as determined by the randomization number.

Monitoring of adherence: Data stored on the Juvent devices will be collected by the study team during the six month visit and twelve month visit via a serial connector. The study team will be able to monitor the date, time and duration of each use. The study coordinator will contact subjects bi-weekly to discuss adherence and to provide support.

Six-month visits: Subjects will return to the study site with their Juvent devices. The study team will collect study data from the device via a serial connector. The study team will also review medical status, supplement compliance and to record any adverse events. Additional calcium carbonate/vitamin D3 will be provided if needed.

Twelve-month visit (study completion): Subjects will return to the study site with their Juvent devices. The study team will collect study data from the device via a serial connector. Subjects will return for DXA of hip and spine, pQCT of the tibia and MRI of tibia and spine, as well as a review of medical status, supplement compliance and any adverse events.

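### Years since menopause is left out of the between-arm analysis: a cheap, conditional precision gain is forgone, but validity is not affected

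*Combined protocol and SAP*

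**What the plan says.** Under Target population the trial takes "Post-menopausal female subjects ages 45-65 years who have a history of amenorrhea for a minimum of 24 months". Key inclusion criteria and the later section on recruitment and eligibility repeat the age range and the 24-month minimum. None of the three sets a maximum time since menopause.

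Under Study procedures, women "will be randomly allocated 1:1 to an active LMMS or a placebo device". The method is that "Random numbers will be generated by a random number generator by the unblinded device manager", with even numbers going to active treatment and odd to placebo. Neither this section nor the separate section on randomization and blinding describes strata or blocks.

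Under Analyses, the outcome analyses test the primary hypothesis (12-month change in distal tibia failure strength) and the secondary hypothesis (vertebral marrow fat) with unpaired t-tests. Regression models of the within-subject change are built in addition, with "an indicator variable for treatment group and baseline measurement as the covariates". Their declared purpose is to see whether the treatment effect relates to the baseline value.

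The descriptive statistics paragraph states: "Baseline characteristics will include distribution of age, race/ethnicity, adherence data and outcome variables". Time since menopause is not named there. The same paragraph also promises summary statistics for every variable measured.

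**The concern.** The endpoint is a one-year change, and the Background gives prevention of bone loss as part of the rationale. Each arm's natural course over the year therefore feeds into the contrast. A woman two years past menopause and one fifteen years past can both be eligible. If the rate of change differs with time since menopause, that variation stays in the residual error of a trial planned around 64 completers, and a chance excess of recently menopausal women in one arm would move the estimate.

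The baseline measurement does not obviously stand in for this. It records where a woman starts, not how fast she is changing. At stake is the width of the confidence interval for the treatment effect, and how credible the result looks if the arms happen to differ on this factor.

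**Working it through.** **Inputs from the documents.** 83 randomized to leave 64 completers (Subjects randomized by Penn researchers); 1:1 allocation, taken here as 32 completers per arm; "two-sided tests of hypotheses and a p-value < 0.05 indicating significance" (Analyses).

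**The plan's own figure.** 64/83 implies a loss of 1 − 64/83 = 22.9%. No dropout rate, effect size, SD or power is given, so neither 64 nor 83 can be rebuilt from stated inputs. The 80% power used below is a reference level, not the plan's.

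**Assumption.** Let r be the correlation between years since menopause and 12-month change that remains once the baseline value is in the model. The documents give no value; 0.1 to 0.4 is shown.

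**Step 1, validity.** Under randomization the factor is balanced in expectation. In 40,000 simulated null trials per setting with 32 per arm, the unadjusted t-test rejected 5.1%, 5.0% and 4.9% of the time for r = 0, 0.3 and 0.5. The type I error holds.

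**Step 2, chance imbalance.** The standardized arm difference in years since menopause has standard error sqrt(2/32) = 0.25 SD. The probability of a difference above 0.25 SD in either direction is 31.7%, and above 0.5 SD it is 4.6%. The 95% limit is 1.96 × 0.25 = 0.49 SD. If the SD were 4 to 5 years (assumed), the standard error would be 1.0 to 1.25 years. A difference at the 95% limit moves the estimated effect by r × 0.49, that is 0.049, 0.098, 0.147 or 0.196 SD of the change for r = 0.1, 0.2, 0.3 or 0.4. The t-test's standard error already allows for this; it is the precision loss seen from another side, not a second cost.

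**Step 3, precision.** Residual variance is multiplied by 1 − r², so the equivalent number of completers is 64/(1 − r²). With two-sided alpha 0.05, the effect detectable at 80% power without the covariate is (1.96 + 0.842) × 0.25 = 0.700 SD. With it, this becomes 0.700 × sqrt(1 − r²), and power at 0.700 SD is Φ(0.700/(0.25 × sqrt(1 − r²)) − 1.96).

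| r | 1 − r² | Equivalent completers | Power at 0.700 SD | Detectable effect (SD) |
|---|---|---|---|---|
| 0.1 | 0.99 | 64.6 | 80.4% | 0.697 |
| 0.2 | 0.96 | 66.7 | 81.6% | 0.686 |
| 0.3 | 0.91 | 70.3 | 83.6% | 0.668 |
| 0.4 | 0.84 | 76.2 | 86.4% | 0.642 |

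**Step 4, price of the covariate.** The table ignores the cost of estimating one more coefficient. With 64 completers and normal covariates, the expected variance inflation is 1 + 1/60 = 61/60 with baseline alone and 1 + 2/59 = 61/59 with both covariates, a ratio of 60/59. Break-even is 1 − r² = 59/60, so r = sqrt(1/60) = 0.13. Net of this cost, the equivalents are 63.6, 65.6, 69.2 and 74.9. At r = 0.1 there is a trivial loss; from 0.2 upwards there is a gain.

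**Step 5, where the covariate acts.** The t-tests carry the hypotheses. A covariate added only to the additional regression leaves the primary p-value unchanged.

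**The case against.** The strongest objection is that nothing in the documents links years since menopause to the rate of change, let alone for MR-based failure strength at the tibia or for marrow fat. A reader might infer that the plan ignores a known driver of bone loss. The documents do not support that: they give no loss rate by years since menopause and no correlation. This objection stands, so the factor can be offered only as plausible, and the size only as a range that includes values where there is no gain.

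A reader might also infer that leaving the factor uncontrolled biases the comparison. It does not; allocation is random, and Step 1 shows the error rate intact.

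Three narrower objections also stand. The 24-month criterion can be met by a yes/no answer, and the visit schedule lists only medical history, so the date of last menses may not be collected at all. The baseline description is not a closed list and promises to tabulate whatever is measured, so the gap there is mainly one of data capture. Substituting age only for women with an unknown date would mix two scales in one covariate.

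What survives is that one prespecified covariate costs very little if it proves useless, and that adding it after an imbalance has been seen would be open to challenge.

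**Conclusion.** The plan is valid on this point, but it forgoes a possible gain in precision that would be cheap to secure. The gain is nil or slightly negative for r below about 0.13, under 2 points of power at r = 0.2, and about 6 points at r = 0.4 (roughly 76 completers' worth of information from 64). It reaches the primary inference only if the adjusted model replaces the t-test as the between-arm test.

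This rests on an assumed r, an equal split of 32 completers per arm, the normal approximation, and r being what is left after the baseline value; if the two overlap, the gain is smaller. Any further gain from moving the baseline value itself into the primary test is not counted here. It belongs among the inexpensive improvements, not the validity errors.

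**What to change.** Before unblinding:

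- Add the year of last menses to the screening history. It will then be summarized by arm under the existing promise to tabulate all measured variables; naming it in the baseline list makes this explicit.
- In the outcome analyses, prespecify a regression of 12-month change on arm, baseline value and years since menopause, for failure strength and for marrow fat.
- State that the arm coefficient from this model is the between-arm test, with the unpaired t-test kept as a supporting analysis.
- If the year cannot be obtained reliably, use age, which is already in the baseline list, as the covariate for all women. Settle this choice without reference to outcome data by arm.

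The cost is one degree of freedom, one history field and a few lines in the analysis section, with no added visit or procedure. The drawback is imprecise recall in some women, for example after hysterectomy, which would weaken the covariate and shrink the gain.

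### The regression of change on arm and baseline has no arm-by-baseline term, so it cannot show whether the treatment effect depends on baseline

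*Combined protocol and SAP*

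**What the plan says.** All of the relevant text is in the Analyses section of the combined protocol and SAP.

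- **Main tests** (Outcome analyses): "Unpaired t-tests will be used to test the primary and secondary hypotheses that the means of the temporal changes are different between treatment groups".
- **Regression, purpose:** "Linear regression models will also be constructed to compare mean within-subject changes between groups".
- **Regression, terms:** the outcome is the within-subject difference, with "an indicator variable for treatment group and baseline measurement as the covariates". No product term is listed.
- **Inference claimed from that regression:** "In this manner we will be able to evaluate whether the treatment effect is associated with baseline values".
- **Other regressions:** one concerns adherence ("we will examine the hypothesis that the treatment effect scales with compliance using regression analysis"). Under Secondary analyses, "associations between baseline parameters as well as between the temporal changes in these parameters will be examined by linear regression". Neither includes an arm-by-baseline term.

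The section on subjects randomized gives 83 women randomized to obtain 64 completers, and allocation is 1:1.

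**The concern.** Whether a treatment effect is associated with baseline is a question of effect modification: does the active-minus-placebo difference in change grow or shrink as baseline failure strength rises? The opening words of the quoted sentence tie the answer to the two-covariate model just described. That model assumes the difference is the same at every baseline value, so it cannot test whether it is.

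The plan does not say which coefficient will be interpreted. The treatment coefficient is a single number, so the baseline coefficient is the one most likely to be read as the answer. That coefficient describes how change relates to baseline in both arms together. Because change is computed from the same baseline measurement, it can differ from zero with an inert device. A report that followed the plan literally could therefore make an unsupported statement about which women benefit.

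**Working it through.** **Structure.** Let D be the 12-month change, A the arm (0 or 1) and X the baseline value.

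- Model in the plan: D = a + b·A + c·X + error. The arm difference at any X is (a + b + cX) − (a + cX) = b, a constant.
- Model that answers the question: D = a + b·A + c·X + d·A·X + error. The arm difference at X is b + dX, so d is the effect modification.

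With 1:1 allocation, c in the first model is close to the average of the two arms' slopes. Slopes of (−0.2, −0.2) and of (−0.45, +0.05) both average −0.2. In one very large simulated data set (200,000, to show the algebra only) both gave the same main-effects fit, b = 0.396 and c = −0.201. The interaction estimates were 0.001 and 0.501. The plan's model cannot tell these two situations apart.

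**Inputs for sizing.** From the documents: 64 completers, 1:1 allocation, two-sided 0.05. Assumed: 32 completers per arm, normal data, and a range for the baseline-to-12-month correlation ρ and the SD ratio r = SD12/SD0, because the documents give neither. There is no figure in the plan to reproduce on this point.

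**False signal when there is no modification.** With an inert device, the slope of D on X is c = ρ·r − 1. In baseline SD units the residual SD is r·√(1 − ρ²), and the standard error of c is about that divided by √64 = 8.

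- ρ = 0.7, r = 1: c = −0.30; SE ≈ √0.51/8 = 0.714/8 = 0.089; ratio ≈ −3.4.
- ρ = 0.9, r = 1: c = −0.10; SE ≈ √0.19/8 = 0.436/8 = 0.054; ratio ≈ −1.8.
- ρ = 0.99, r = 1.1: c = 1.089 − 1 = +0.089; SE ≈ 1.1 × √0.0199/8 = 0.155/8 = 0.019; ratio ≈ +4.6.

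Percentage of simulated trials with p < 0.05 for the baseline coefficient (20,000 per cell):

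| SD12/SD0 | ρ=0.7 | 0.8 | 0.9 | 0.95 | 0.98 | 0.99 |
|---|---|---|---|---|---|---|
| 1.0 | 89 | 73 | 42 | 24 | 12 | 8 |
| 1.1 | 61 | 30 | 5 | 18 | 78 | 99 |
| 0.9 | 99 | 97 | 96 | 97 | 100 | 100 |

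In the 1.1 row the slope is positive from ρ = 0.95 upward. The interaction test rejects in 4.6% to 5.3% of trials in all 18 cells.

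**Missed signal when modification is real.** Take a true slope difference of 0.5 residual SD per baseline SD.

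- Slopes −0.25 and +0.25: c averages 0.001 and is significant in 5.2% of trials. The interaction test has about 48% power.
- The whole 0.5 in one arm (slopes 0 and 0.5, or −0.5 and 0): c is significant in about 47% of trials, much like the interaction test. For slopes 0 and 0.5, c estimates (0 + 0.5)/2 = 0.25, the value that a common slope of 0.25 with no modification would also give.

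**What the interaction term can deliver.** Its standard error is about √(1/32 + 1/32) = 0.25 residual SD per baseline SD. The normal approximation puts 80% power at (1.96 + 0.84) × 0.25 = 0.70. Simulation, which allows for estimated variances, is slightly less favourable: power is 21% at 0.3, 48% at 0.5, 75% at 0.7 and 80% at about 0.75. The mean 95% CI half-width is about 0.52.

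**The case against.** The strongest reply is that nothing important rests on the sentence. Effect modification by baseline is not among the objectives, the listed outcomes, or the primary and secondary hypotheses. The regression's main stated purpose, comparing mean change between arms, is met by the listed covariates. This is correct, and it limits the weight of the point.

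The sentence may also be loose wording for a treatment effect adjusted for baseline, or for an association between change and baseline. That is possible, but the text refers to the treatment effect. If another meaning was intended, the sentence still needs rewording.

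The percentages describe a misreading that the plan does not say it will make, and they depend on assumed inputs. They show how badly the baseline coefficient could mislead; they do not predict this trial. The 5% figure for missed modification is the extreme case of cancelling slopes, so it should be read beside the 47% for a slope in one arm only.

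Finally, an interaction test with 64 completers would rarely settle the question. The answer also depends on scale: the Descriptive statistics paragraph calculates both differences and percentage changes, and an interaction on one can vanish on the other. Both points stand. They argue for an exploratory label and a stated scale, or for deleting the sentence. They do not make the present model able to answer the question.

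**Conclusion.** The concern holds. As written, the plan promises an assessment that its stated model cannot provide, and no other analysis in the documents supplies it. This follows from the listed covariates and needs no assumption about the data.

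The size of any resulting error does rest on assumptions. With no modification, the baseline coefficient is significant in anywhere from 5% to 100% of trials over correlations of 0.7 to 0.99 and SD ratios of 0.9 to 1.1. With real modification of 0.5 residual SD per baseline SD, it is significant in about 5% to 47%, depending on how the slopes divide between the arms.

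The scope is narrow. The t-tests of the primary and secondary hypotheses and the baseline-adjusted treatment estimate stand as planned. The sentence should be corrected, but it does not threaten the main result.

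**What to change.** Keep the two-covariate model for the baseline-adjusted treatment estimate, then do one of the following.

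1. **If the question is of interest,** add a second model with a centred-baseline-by-arm term and move the quoted sentence to it. Base any statement about dependence on baseline on that term's estimate and 95% CI. Label the analysis exploratory and name the scale; the within-subject difference already specified as the outcome is the natural choice.
2. **If it is not,** delete the sentence, or reword it to say that the model gives a treatment effect adjusted for baseline.

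The cost is one model term and one moved sentence, or one deletion. No new data or visits are needed, and the primary test does not change. The drawback of the first option is low precision: the report should say that a non-significant interaction does not show a constant effect.
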